12.2 Sample Size and Power Calculations

Double-blind Period

In a Japanese Phase 2 clinical study (MR13A9-4), a mean difference of -1.0 was observed between the difelikefalin and placebo groups with an SD of 2.09 and 1.98 in the difelikefalin and placebo group, respectively, regarding the change from baseline in the weekly mean of the daily 24-hour WI-NRS score at end of Week 4.

In the pooled data of 2 Phase 2 clinical studies (CLIN3102 and CLIN3103), a mean difference of -0.8 was observed between difelikefalin and placebo group with an SD of 2.15 and 1.99 in the difelikefalin and placebo group, respectively, regarding the change from baseline in the weekly mean of the daily 24-hour WI-NRS score at end of Week 4.

Based on the results observed at the end of Week 4 in previous studies as mentioned in the above paragraphs, a mean difference of -0.9 with a common SD of 2.1 is assumed between difelikefalin and placebo group regarding the primary endpoint. Assuming a 2-sided significance level of 5% and a statistical power of 90%, 116 subjects per group will be required to detect a difference of -0.9, with a common SD of 2.1, between the difelikefalin and the placebo group using a 2-sample t-test. In addition, assuming, a 10% drop out rate, 258 subjects in total need to be enrolled in the double-blind study period, i.e., 129 subjects per group.

The sample size calculation was done with the software nQuery Version 8.6 using a 2-sample t-test to compare means.

Open-label Extension Period

All subjects who completed the double-blind period may continue into the 14-week open-label extension period if they meet the eligibility criteria at Day 1 of the open-label extension period.

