12.3 Randomisation

All subjects enrolled must be identifiable throughout the study.

Randomisation of subjects will be performed on Day 1 before start of treatment with study drug.

Each eligible subject will be randomised during the double-blind period in a 1:1 allocation ratio to receive either difelikefalin or matching placebo using a validated centralised procedure (IWRS) that automates the random assignment of treatment groups to randomisation numbers. Subjects will be stratified according to their use or non-use of concomitant medications to treat their itch (refer to Section 6.8.1) during the week prior to randomisation (run-in period) as well as the presence or absence of specific medical conditions. These specific medical conditions include:

- History of fall or fracture (related to fall)
- Confusional state or mental status change or altered mental status or disorientation
- Gait disturbance or movement disorder

Randomised subjects who terminate their study participation for any reason regardless of whether the investigational product was taken or not, will retain their randomisation number. The next subject will be given the next randomisation number.

Before the start of the study, a randomisation list will be created for each stratum. The randomisation lists will be kept strictly confidential, accessible only to authorised persons, until the time of unblinding.

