12.8 Efficacy Evaluations

12.8.1 Primary Efficacy Evaluations

The primary efficacy endpoint is defined as the change from baseline in the weekly mean of the daily 24-hour WI-NRS score at Week 4 (Days 23 to 29) of the double-blind period. The FAS will be used as the primary population for the analysis of the primary efficacy endpoint as well as for its sensitivity analysis. The PPS will be used as a secondary population.

The weekly mean of the 24-hour WI-NRS score will be defined as the sum of the daily WI-NRS score reported during a specific week during the double-blind period (e.g., Days 2 to 8, Days 9 to 15, Days 16 to 22, Days 23 to 29) divided by the number of days with non-missing scores for that week. If the daily WI-NRS is missing for >3 days during a specific week, the corresponding weekly mean WI-NRS will be set to missing. The baseline score will be defined as the average of the daily 24-hour WI-NRS scores collected over the run-in period, including pre-randomisation assessments collected on Day 1.

The change from baseline in the weekly mean of the daily 24-hour WI-NRS score at Week 4 (Days 23 to 29) of the double-blind period will be analysed using a MMRM. Missing scores will not be imputed. Assuming that the data are MAR, the estimates of the treatment differences calculated from the MMRM described below are unbiased. The model will contain treatment, week, and treatment-by-week interaction as fixed effects; baseline NRS score, use of prior anti-itch medication and presence of specific medical conditions as covariates.

Repeated measures will include values collected at the end of Weeks 1, 2, 3, and 4.

An unstructured covariance matrix will be used to model the within-subject errors. Should the model fail to converge, a compound symmetric covariance matrix will be used instead.

The Kenward-Roger2 approximation will be used to estimate the denominator degrees of freedom.

Standard descriptive statistics will be reported on the values and changes from baseline at Week 4 of the double-blind period along with the adjusted mean change at Week 4 for each group and its 2-sided 95% CI. The adjusted mean treatment difference in the change between difelikefalin and placebo groups will be estimated at Week 4 of the double-blind period as the simple contrast in the treatment effect. Its 2-sided 95% CI as well as its p-value will be presented

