Testing of the primary efficacy endpoint will be 2-sided and conducted at the 5% error level. The null hypothesis in this study is that there is no treatment difference in the primary efficacy analysis of the primary endpoint, i.e., the change from baseline in the weekly mean of the daily 24-hour WI-NRS score at Week 4 of the double-blind period. The alternative hypothesis is that subjects randomised to difelikefalin experience significantly less itching compared to subjects randomised to placebo.

In the primary efficacy analysis, missing NRS data will not be imputed.

Sensitivity analyses of the primary efficacy endpoint will be conducted to evaluate the robustness of study results under different assumptions and imputation algorithms.

For both sensitivity analyses described below, the adjusted mean change at Week 4 for each group and its 2-sided 95% CI, the adjusted mean treatment difference in the change between difelikefalin and placebo groups at Week 4 of the double-blind period, its 2-sided 95% CI as well as its p-value will be estimated as in the primary efficacy analysis.

Sensitivity 1: Multiple Imputation (MI) – MMRM

Multiple imputed data will be generated using the approach described below. Each imputation data will be analysed using the same MMRM model as the one used for the primary efficacy analysis, and the results of the analyses will be combined. Imputation will be performed using all available data collected at each time point between Week 1 and Week 4 of the double-blind period.

- Intermittent missing NRS scores will first be imputed using the Markov Chain Monte Carlo method implemented with the SAS MI procedure, which is appropriate for non-monotonic missing data.
- The monotone missing NRS values will then be multiply imputed with the SAS MI procedure using the monotone regression method.

- For each stage, MI will be performed within treatment group with covariates for baseline NRS score, both randomisation stratification factors and all non-missing NRS scores for each week. Should convergence issues occur due to small cell size for the categorical covariates corresponding to strata (at either stage), those specific covariates will be removed from the model.

Sensitivity 2: Placebo MI – MMRM

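### If the unstructured MMRM does not converge, the only stated fallback is compound symmetry with model-based standard errors, which runs the Week 4 test above 5% if spread grows over Weeks 1 to 4: an unlikely trigger, but a cheap repair

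*Protocol*

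**What the plan says.** Protocol 12.8.1, repeated in the synopsis, fits an MMRM to the change in weekly mean WI-NRS at Weeks 1, 2, 3 and 4 and takes the treatment contrast at Week 4. The first-choice covariance is unstructured. The fallback is one sentence: "Should the model fail to converge, a compound symmetric covariance matrix will be used instead". Kenward-Roger2 is the only adjustment named. No structure with week-specific variances, no intermediate step and no empirical standard error appears. On the error rate the section says: "Testing of the primary efficacy endpoint will be 2-sided and conducted at the 5% error level".

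Both multiple-imputation sensitivity analyses in 12.8.1 reuse the primary MMRM.

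The same one-step rule appears elsewhere:
- Protocol 12.8.2 states it for the 5-D itch and Skindex-10 models.
- Protocol 12.8.2 analyses weekly WI-NRS over 12 weeks by a method described only as similar to the primary one, so there the rule applies by inference.
- SAP 4.7.1 repeats it for the open-label models, and SAP 4.7.2 carries it to Skindex-10.

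SAP section 1 says that the double-blind analyses are in a separate SAP. That document was not among those supplied.

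**The concern.** In its standard meaning, compound symmetry has one variance and one covariance; the version with a separate variance per occasion is a different, separately named structure. The primary contrast sits at Week 4 alone, but under this fallback its standard error is built from the average variance of Weeks 1 to 4. Change from baseline often spreads out as subjects diverge. If it does so here, the average lies below the Week 4 variance, the confidence interval is too narrow, and the test rejects too often at the one time point that counts. Kenward-Roger2 does not correct a wrong variance structure. The sensitivity analyses would share the defect if they used the same fallback, so they could not reveal it.

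**Working it through.** **1. The plan's own figure.** Protocol 12.2 states: "a mean difference of -0.9 with a common SD of 2.1 is assumed between difelikefalin and placebo group", and "Assuming a 2-sided significance level of 5% and a statistical power of 90%, 116 subjects per group will be required". With difference 0.9, SD 2.1, two-sided 5% and 90% power, the normal approximation gives 115 per group. The exact t-test calculation gives 116, with power 90.15%. Then 116/0.90 = 128.9, so 129 per group and 258 in total. The sample size reproduces and is not in dispute.

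**2. Formula.** With complete data and n per group:
- true SE at Week 4 = SD4 × √(2/n) = 2.1 × √(2/116) = 0.276
- compound-symmetry SE = √(mean of the four weekly variances) × √(2/n)
- ratio r = √(mean variance)/SD4
- actual two-sided level = 2 × [1 − Φ(1.96 × r)]

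The variances that matter are the model's residual variances. The planning SD of 2.1 stands in for the Week 4 value.

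**3. Results.** The SDs at Weeks 1 to 3 are assumed; Week 4 is held at 2.1.

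| Assumed SDs, Weeks 1 to 4 | Mean variance | r | SE used | Actual level |
|---|---|---|---|---|
| 2.1 / 2.1 / 2.1 / 2.1 | 4.410 | 1.000 | 0.276 | 5.0% |
| 1.8 / 1.95 / 2.05 / 2.1 | 3.914 | 0.942 | 0.260 | 6.5% |
| 1.8 / 1.9 / 2.0 / 2.1 | 3.815 | 0.930 | 0.257 | 6.8% |
| 1.5 / 1.8 / 2.0 / 2.1 | 3.475 | 0.888 | 0.245 | 8.2% |
| 1.2 / 1.6 / 1.9 / 2.1 | 3.005 | 0.826 | 0.228 | 10.6% |
| 1.0 / 1.5 / 1.9 / 2.1 | 2.818 | 0.799 | 0.220 | 11.7% |
| 1.0 / 1.4 / 1.8 / 2.1 | 2.653 | 0.776 | 0.214 | 12.9% |
| 2.4 / 2.3 / 2.2 / 2.1 | 5.075 | 1.073 | 0.296 | 3.6% |

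Example, third row: (3.24 + 3.61 + 4.00 + 4.41)/4 = 3.815; √3.815 = 1.953; 1.953/2.1 = 0.930; 2 × [1 − Φ(1.823)] = 6.8%.

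**4. Simulation.** Compound symmetry was fitted by REML to 258 subjects with 10% monotone dropout, 4,000 runs per scenario, and true correlation either exchangeable (0.7) or autoregressive (0.85). The model had week and treatment-by-week terms only, and the critical value was fixed at 1.965. The Monte Carlo standard error near 5% is √(0.05 × 0.95/4000) = 0.3 percentage points. Six of the patterns above were run:
- constant: 4.5% to 4.8%
- 1.8 / 1.9 / 2.0: 6.5% to 7.0%
- 1.5 / 1.8 / 2.0: 8.5% to 8.9%
- 1.2 / 1.6 / 1.9: 10.9% to 11.1%
- 1.0 / 1.4 / 1.8: 13.8% to 14.1%
- falling: 3.2%

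The same fits with a sandwich standard error gave 4.1% to 5.5% in every scenario.

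**5. Which pattern is likely?** The documents give only a weak hint. In the Japanese Phase 2 study MR13A9-4, Week 4 results came "with an SD of 2.09 and 1.98 in the difelikefalin and placebo group, respectively". Protocol 1.2.2.3 gives Week 8 standard errors of 0.30 (0.5 µg/kg) and 0.29 (placebo). With 61 subjects on 0.5 µg/kg and 247 − 184 = 63 on placebo, the implied Week 8 SDs are 0.30 × √61 = 2.34 and 0.29 × √63 = 2.30. That is growth of about 12% (2.34/2.09) and 16% (2.30/1.98) over four weeks. These are standard errors of adjusted means and cover Weeks 4 to 8, not Weeks 1 to 4. Growth of about that size (1.85 / 1.93 / 2.02 / 2.1) gives 6.5%.

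**6. How likely is the trigger?** An unstructured matrix for k visits has k(k+1)/2 parameters:
- primary model, 4 visits: 10
- QoL models in 12.8.2, 3 post-baseline visits: 6
- SAP models pooling both periods, 7 visits: 28
- 12-week WI-NRS model: 78

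If the primary model had a 1% chance of failing (assumed), the overall level would be 0.99 × 5% + 0.01 × 6.8% = 5.02% under mild growth, and 0.99 × 5% + 0.01 × 12.9% = 5.08% under the steepest pattern.

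**The case against.** The strongest reply is that the fallback will hardly ever be used. In a small simulation, unstructured models for 258 subjects with dropout and intermittent gaps converged in 600 of 600 runs with 4 visits and in 50 of 50 with 12 visits. It used maximum likelihood with Fisher scoring rather than SAS REML, and 50 runs is a thin check, but it agrees with experience for the primary model. This stands.

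It is also fair that every inflated figure rests on assumed SDs. The steepest patterns need the SD to double in three weeks, the documentary hint points to the mild end, and a falling SD makes the test conservative. This stands too.

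Four stronger readings are tempting, and the documents do not support them:
- **A reader might infer that the primary 5% level is broken.** It is exceeded only if the model fails to converge and spread also grows.
- **A reader might infer that no other fallback exists.** Protocol 12.1 calls its text a general description, and the double-blind SAP could add steps.
- **A reader might infer that the 12-week model will fail.** Its 78 parameters make failure less remote, but nothing shows that it is likely. That endpoint is also secondary, and 12.8.2 says that no single significant result will be given undue weight.
- **A reader might carry the 5% claim into the open-label SAP.** SAP 4.7.1 plans within-sequence estimates and confidence intervals and specifies no between-sequence test, so only interval coverage is at issue.

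The reply does not touch the algebra. Where the fallback is needed and spread grows, the stated rule errs in the anti-conservative direction.

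**Conclusion.** This is a cheap improvement to a rule with a low probability of use. Conditional on non-convergence and on SD rising from Week 1 to Week 4, the nominal two-sided 5% test runs at about 6.5% to 7% under mild growth and about 8% to 12% under steeper assumed growth; the most extreme pattern tried gave 12.9% by formula and up to 14.1% in simulation. Unconditionally, the primary error rate hardly moves: 5.02% to 5.08% at an assumed 1% failure rate. For the 12-week WI-NRS model, where the rule is inferred, rising SDs would make early-week intervals too wide and late-week intervals too narrow; the size depends on the shape of the growth, which is unknown. The conclusion rests on the standard one-variance meaning of compound symmetry, on assumed SDs for Weeks 1 to 3, and on the supplied documents alone.

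**What to change.** Replace the single fallback with an ordered sequence of structures that keep a separate variance for each week: for example heterogeneous Toeplitz, then heterogeneous AR(1) or heterogeneous compound symmetry. If homogeneous compound symmetry is kept as the last step, pair it with an empirical (sandwich) standard error and state the degrees-of-freedom method. State whether the rule covers the 12-week WI-NRS model, and whether the sensitivity analyses use the structure finally chosen for the primary model. Use the same wording in Protocol 12.8.1 and 12.8.2 and in SAP 4.7.

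The cost is a short text change, and Kenward-Roger2 has to be replaced wherever the sandwich standard error is used. A protocol amendment needs regulatory and ethics review (Protocol 16.2), and the open-label SAP is already final at version 2.0, so the double-blind SAP may be the simpler place if it is still open. If the analyses have already been run, report which covariance structure each model used, and add a week-specific-variance or sandwich analysis wherever compound symmetry was used.

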12.8.2 Secondary Efficacy Evaluations

Secondary and other efficacy endpoints will be analysed using the FAS, as the primary population, and PPS, as a secondary population.

Significance level is set at an alpha of 0.05 (2-sided) and no adjustment will be made for testing multiple secondary outcomes. Some significant findings are expected to occur by chance so undue consideration will not be given to any particular significant difference. Moreover, interpretation of the results will be based on patterns of differences and in conjunction with the results of the primary analyses.

The proportion of subjects achieving ≥ 3 -point and ≥ 4 -point improvement, respectively, from baseline with respect to the weekly mean of the daily 24-hour WI-NRS at Week 4, 8 and 12 of the double-blind period will be analysed using a logistic regression model containing terms for treatment group, baseline WI-NRS score, use of prior anti-itch

medication, and presence of specific medical conditions. Missing NRS data will be imputed using a MI approach, assuming that subjects who discontinue double-blind period early would have similar WI-NRS scores as other subjects in their respective treatment arm that have complete data. The observed number and proportion of subjects with ≥ 3 -point and ≥ 4 -point improvement, respectively, among the non-imputed data will be reported along with the imputed data logistic regression model-based estimates of the proportions of responders (as defined above) with their 2-sided 95% CIs, odds ratio as well as 2-sided Wald 95% CIs and p-value. A sensitivity analysis will be performed. The same logistic regression model will be used as the one specified above; the only difference is that subjects who discontinue investigational product early will be considered non-responders. Further details will be specified in the SAP.

Change from baseline in itch-related QoL at end of Week 12 of the double-blind period, as assessed by the 5-D itch scale total score will be analysed using a MMRM. Missing scores will not be imputed. Assuming that the data are MAR, the estimates of the treatment differences calculated from the MMRM described below are unbiased. The model will contain treatment, week, and treatment-by-week interaction as fixed effects; baseline score, use of prior anti-itch medication and presence of specific medical conditions as covariates. The baseline 5-D total score will be defined as the value collected on Day 1, prior to randomisation. Repeated measures will include values collected at each time point of the double-blind period. An unstructured covariance matrix will be used to model the within-subject errors. Should the model fail to converge, a compound symmetric covariance matrix will be used instead. The Kenward-Roger2 approximation will be used to estimate the denominator degrees of freedom. Standard descriptive statistics will be reported on the values and changes from baseline at end of Week 12 along with the adjusted mean at end of Week 12 for each group and its 2-sided 95% CI. The adjusted mean treatment difference between difelikefalin and placebo groups will be estimated at end of Week 12 of the double-blind period as the simple contrast in the treatment effect as well as its 2-sided 95% CI and its p-value.

Change from baseline in itch-related QoL at end of Week 12 of the double-blind period, as assessed by the Skindex-10 scale total score will be analysed using the same approach as described above fitted for the change from baseline in itch-related QoL at end of Week 12 of the double-blind period, as assessed by the 5-D itch scale total score. The baseline Skindex-10 scale total score will be defined as the value collected on Day 1, prior to randomisation.

Change from baseline in the weekly mean of the 24-hour WI-NRS score at each week of the double-blind period will be analysed following a methodology similar to the one employed for the primary analysis of the primary efficacy endpoint. Repeated measures will include values collected at the end of each week from Week 1 until Week 12 of the double-blind period.

Change from baseline in itch-related QoL at each time point of the double-blind period and of the open-label extension period, as assessed by the Skindex-10 scale total score will be

analysed using the same approach as described above fitted for the change from baseline in itch-related QoL at end of Week 12 of the double-blind period, as assessed by the 5-D itch scale total score. Repeated measures will include all values collected during each period separately.

Change from baseline in itch-related QoL at each time point of the double-blind period and of the open-label extension period, as assessed by the 5-D itch scale total score will be analysed separately using the same approach as described above fitted for the change from baseline in itch-related QoL at end of Week 12 of the double-blind period, as assessed by the 5-D itch scale total score. Repeated measures will include all values collected during each period separately.

The number and percentage of subjects for each response of the Patient Global Impression of Change will be reported as well as the count of subjects with missing values. The number and percentage of subjects who rate their itch condition as “Very much improved” or “Much Improved” at the end of Week 12 of the double-blind period/end of double-blind will be reported together. The Mantel-Haenszel estimate, adjusting for the randomisation stratification variables, of common odds ratio with its 2-sided 95% CI will be reported. Additionally, the 2-sided exact Clopper Pearson 95% CI for the proportion of subjects who rate their itch condition as “Very much improved” or “Much Improved” will be presented.

12.9 Safety Evaluations

The objective of the evaluation of the safety variables is to investigate the data for any effects on clinical tolerability and laboratory safety variables. All such variables will be summarised by treatment group and by study period (and time point as appropriate). No inferential statistics are planned. Safety data will be summarised descriptively.

12.9.1 Adverse Events

All AEs and pre-treatment AEs will be coded using MedDRA to MedDRA SOC and PT for standardisation and summary purposes.

All reported AEs will be included in summary tables by treatment group and by study period, as appropriate. AEs will also be presented in by-subject AE listings.

AEs relative to the double-blind period are identified as any AE:

- With an onset date after the first dose of the investigational product in the double-blind period for subjects who do not enter the open-label extension period.
- With an onset date after the first dose of the investigational product in the double-blind period up to the first dose of difelikefalin in the open-label extension period for subjects who continue into the open-label extension period.

AEs relative to the open-label extension period are identified as any AE with an onset date after the first dose of difelikefalin in the open-label extension period.

A pre-treatment AE is defined as any AE that has an onset before the first investigational product administration.

The number and percentage of subjects experiencing AEs will be summarised by treatment group and by study period. A subject will be counted only once in the incidence count for a MedDRA SOC or PT, although a subject may have multiple occurrences (start and stop) of an event associated with a specific MedDRA SOC or PT.

The incidence and percentage of subjects experiencing treatment-emergent SAEs and AEs leading to investigational product discontinuation will be presented by the appropriate MedDRA SOC and PT.

AEs will also be summarised by severity and by relationship to investigational product for each study period. If the severity and/or relationship to the investigational product of an AE is missing, a worst-case scenario will be assumed (i.e., the AE will be categorised as “severe” and/or “related” to the investigational product). If a subject reports the same AE multiple times the event with the worst severity and the strongest relationship to investigational product will be tabulated.

For each study period, an overall summary table will be provided, presenting for each treatment group, the number and percentage of subjects as well as the number of events for AEs, SAEs, treatment-emergent deaths, treatment-related AEs, treatment-related SAEs, severe AEs, AEs leading to investigational product interruption, AEs leading to investigational product discontinuation and AESIs.

In addition, the following summary tables will be presented and will include the number and percentage of subjects as well as the number of events for:

- AEs by SOC and PT
- SAEs by SOC and PT
- AEs by SOC, PT, and maximum severity
- Related AEs by SOC and PT
- AEs leading to investigational product discontinuation by SOC and PT
- Most common AEs ($\geq 2\%$ or more of subjects in any treatment group) by PT
- AESIs by PT
- Related AESIs by PT

All AEs will be listed in chronological order, including information such as treatment group/treatment sequence, subject identifier, age, sex, use/non-use of anti-itch medication,

presence/absence of specific medical conditions a flag indicating whether the AE was relative to the double-blind or to the open-label extension period, and all related AE status information (start and stop dates, whether the event was ongoing, study day of onset, severity, seriousness, relationship to study medication, action taken with study treatment, and outcome). Separate listings will be generated for SAEs, deaths, AEs leading to investigational product discontinuation, and pre-treatment AEs. Pre-treatment AEs will not be included in any summary tables.

